5.2 Exclusion Criteria

1. Coma on admission (Glasgow Coma Scale $<$ 8), need for intubation upon ED arrival, or transferred patients who present previously intubated.
2. Severe agitation or seizures on admission that preclude safe vascular access.
3. Loss of airway protective reflexes and/or vomiting on admission.
4. Predicted or known difficult airway.
5. Pre-existing neurological or psychiatric disease that would confound the neurological or functional evaluations, e.g. dementia.
6. Presumed septic embolus, or suspicion of bacterial endocarditis
7. Currently participating or has participated in any investigational drug or device study within 30 days.
8. Inability to follow-up for 90-day assessment.
9. Known history of allergy to anesthesia drugs.
10. Known history or family history of malignant hyperthermia

5.3 Crossover Criteria

1. Severe agitation or seizures.
2. Loss of airway protective reflexes, vomiting, or aspiration.
3. Inability to maintain airway.
4. Loss of consciousness.
5. Hemodynamic instability.
6. Determination by anesthesiologist and/or neurointerventionalist that randomized method of anesthesia is contraindicated for some other reason (see section 5.4)

5.4 NPO Status

Lack of confirmation of duration of fasting status (*nil per os; NPO*) shall, in and of itself, not be considered a contraindication to moderate sedation for the purposes of this study. Patients should not be excluded from the study or crossed-over from sedation to GA solely due to NPO status.

Rationale:

NPO status is often unknown in patients presenting with acute ischemic stroke. Despite this, the recommendation by the AHA/ASA is that moderate sedation is preferred over general anesthesia for EVT³¹ and this is routinely practiced at stroke centers across the country. The determination of a potential subject's eligibility for sedation should be based on the overall clinical picture, other risk factors for pulmonary aspiration, and consideration of the target depth of sedation for this procedure (moderate sedation).

EVT for acute ischemic stroke is an emergency procedure. The American Society of Anesthesiologists' guidelines for pre-procedural fasting are intended for elective procedures³², and the guidelines for procedural sedation state that "the literature does not provide sufficient evidence that pre-procedure fasting results in a decreased incidence of adverse outcomes in patients undergoing either moderate or deep sedation," leading the task force to conclude that "in urgent, emergent, or other situations in which gastric emptying is impaired, the potential for pulmonary aspiration of gastric contents must be considered in determining (1) the target level of sedation, (2) whether the procedure should be delayed, or (3) whether the trachea should be protected by intubation."³³ The American College of Emergency Physicians has developed specific guidelines that support the use of extended-duration moderate sedation for standard-risk patients undergoing urgent procedures, and for high-risk patients undergoing emergency procedures.³⁴ See Appendix III.

6.0 STUDY PROCEDURES

All subjects who are enrolled into the trial will be followed for 90 days (± 10) unless they withdraw early from the trial, expire before the 90 day follow up window is reached, or are lost to follow up. The study event schedule is illustrated in Table 2.

6.1 Informed Consent

Written informed consent or electronic consent will be obtained for all subjects who are screened and meet the trial inclusion/exclusion criteria. If sites choose to utilize electronic consent, the method of electronic consent used will be based on each individual institution's choice, as approved by the site's IRB. In the event that IRBs of participating centers determine the trial meets criteria for exception from informed consent (EFIC), sites will have the option to pursue local procedures to include community consultation, etc. Below, we provide explanations that justify the use of delayed or exception from informed consent in this particular population.

The trial compares two anesthesia approaches for EVT delivered as usual care. We have demonstrated clinical equipoise in participating stroke centers of excellence. Therefore, the trial meets criteria for comparative effectiveness research. Participation in SEGA should never delay the time-sensitive nature of providing emergent reperfusion therapy in acute ischemic stroke. In addition, a significant proportion of these severe stroke patients are air-transported to the comprehensive stroke centers (CSC) and family members must drive from the outlying hospital to the CSC. Due to the expected stroke severity routinely encountered with proximal intracranial occlusions, the majority of patients will be suffering from either aphasia (language disturbance of either comprehension or expression) or severe neglect (inability to understand or acknowledge they are suffering a stroke). Hence, the majority of patients will be unable to provide informed consent due to lack of capacity. Unfortunately, the majority of legal next of kin fail to arrive before the commencement of EVT procedures; including the transfer from the emergency department to the angio suite for EVT.

As a result, traditional written approach to informed consent in this patient population is rarely feasible and will impact study recruitment, results and generalizability. First, the trial would recruit at a very slow pace and enrollments will be predominantly a less-severe subpopulation of strokes. Second, it is well established across clinical research that the patients who benefit the most from effective interventions are usually those most severely affected. Thus, our estimations of treatment differences would result in decreased probability of observing a difference between the study arms.

Critically, traditional written emergent consent will inherently delay EVT procedures and possibly result in worse clinical outcomes. Pooled analyses from EVT RCTs have demonstrated that minor delays to arterial reperfusion of 20 minutes are associated with worse clinical outcomes. Third, participation in a clinical trial could directly benefit the patient and ultimately society if a new treatment is discovered. The inability to participate in promising research for the most severely affected patients is sometimes interpreted as a breach of the ethical principle of justice. The basic concept of distributive justice, as it relates to clinical research, should not categorically exclude certain subgroups with clinically relevant characteristics such as disease severity, sex, age, etc. This discrimination is unjust and results in skewed generalizable knowledge that guides health care practices.

We recognize that emergency research such as this trial or any research that requires study-related research outcomes will require subsequent written consent from the patient or legal next of kin. Therefore, each site must make a reasonable attempt to reach family members that are available in the hospital or will be arriving within 15 minutes. For patients enrolled via EFIC, explicit written consent must be obtained during the study period of 90-days. Usually, this should occur within 5 days of enrollment during the hospitalization. Ultimately, each participating center must follow their local IRB's decision regarding consent in this trial

Table 2. Schedule of events.

ASSESSMENTS	VISITS				
	Baseline	<16 hours from stroke onset/LSN	18-36 hours	Day 7 or discharge, whichever occurs first	90 ± 15 days
Demographics	Y		Y		
Medical History	Y				
Stroke History	Y		Y		
mRS	Y			Y*	Y
EQ-5D					Y*
NIHSS	Y		Y	Y	
EVT Procedure Variables		Y			
Imaging assessment Parenchymal - CT or MRI Arterial – CTA or MRA	Y Y		Y		
Assess for adverse events		Y	Y	Y	

Note: Except those notated by *, all procedures and assessments are collected a usual care for acute ischemic stroke patients.

6.2 Treatment Period

6.2.1 Endovascular Procedure and Time Metrics

As recommended by the AHA/ASA, the first line therapeutic embolectomy device should be a stent retriever. The use of a proximal balloon guide catheter or a large-bore distal-access catheter, rather than a cervical guide catheter alone, in conjunction with stent retrievers may be beneficial. Future studies should examine which systems provide the highest recanalization rates with the lowest risk for nontarget embolization

Additional EVT therapies including, but not limited to, intra- or extracranial angioplasty ± stenting; antithrombotics (oral, IV or IA antiplatelets or anticoagulants) intra-arterial thrombolytics; are left to the decision of the local treatment team. Conversely, in general, off-label use or therapies not supported by scientific evidence are discouraged. Importantly, the use of these therapies will not be considered a protocol deviation.

Time to reperfusion in EVT trials is correlated with improved outcomes and societies have published position statements on timing metrics. The current protocol provides guidance for centers derived from these recommendations (see table 3).²⁶

Table 3. SEGA recommended guidelines for timing metrics

Acute Stroke Time Metric	Maximal Target Time
Door to Imaging (parenchymal imaging – non-contrast CT, MRI)	15 minutes
Door to IV-tPA bolus/ TNKase	60 minutes
Door to Groin Puncture	90 minutes
Angiosuite arrival to Groin Puncture	20 minutes
Door to Reperfusion	150 minutes IRB NUMBER : HSC-MS-17-0436

The following intra-procedure (thrombectomy) variables will be collected (see CRFs for further details):

- Door to puncture time
- Decision of intervention to puncture time
- Time from puncture to first recanalization attempt
- Time to Revascularization: defined as arterial puncture to TICI $\geq 2b$ revascularization or end of procedure.
- Revascularization assessment at the end of the procedure (using Thrombolysis in Cerebral) Infarction (TICI) score.
- Number of recanalization attempts (i.e. thrombectomy attempts or stent-retriever passes)
- Name of the mechanical retrieval device used
- Utilization of aspiration technique
- Failure to reach clot

6.2.2 Angiographic measures of arterial perfusion and collaterals

Using angiography, the modified TICI (mTICI) score is defined according to the level of blood flow through an occlusion site and consists of 5 discrete categories (table 4a).

Table 4a. Angiographic scoring of large vessel occlusions and reperfusion.

mTICI score	Definition
0	No Perfusion - No antegrade flow beyond the point of occlusion
1	Penetration with Minimal Perfusion - The contrast material passes beyond the area of obstruction but fails to opacify the entire cerebral bed distal to the obstruction for the duration of the angiographic run.
2	Partial Perfusion - Contrast material passes beyond the obstruction and opacifies the arterial bed distal to the obstruction; However, the rate of entry of contrast into the vessel distal to the obstruction and/or its rate of clearance from the distal bed are perceptibly slower than its entry into and/or clearance from comparable areas not perfused by the previously occluded vessel, e.g., the opposite cerebral artery or the arterial bed proximal to the obstruction. 
 • 2a Only partial filling (< 50%) of the entire vascular territory is visualized. • 2b Filling of > 50% all of the expected vascular territory is visualized, but the filling is slower than normal.
3	Complete Perfusion - Antegrade flow into the bed distal to the obstruction occurs as promptly as into the obstruction and clearance of contrast material from the involved bed is as rapid as from an uninvolved other bed of the same vessel or the opposite cerebral artery.

Cerebral collaterals play a key role in determining outcome in endovascular treatments for acute ischemic stroke. In addition, given the hypothesized effect of general anesthesia on blood pressure and cerebral perfusion, collateral grade may be a particularly relevant determinant of outcome in this cohort. Collaterals will be graded from the angiograms by society guidelines, as shown in Table 4b ²⁵

Table 4b. Angiographic scoring of cerebral collaterals

Collateral score	Definition
0	No collaterals visible to the ischemic site.
1	Slow collaterals to the periphery of the ischemic site with persistence of some of the defect.
2	Rapid collaterals to the periphery of the ischemic site with persistence of some of the defect and to only a portion of the ischemic territory.
3	Collaterals with slow but complete angiographic blood flow to the ischemic bed by the late venous phase.
4	Complete and rapid collateral blood flow to the vascular bed in the entire ischemic territory by retrograde perfusion.

6.3 90-day (\pm 15 days) Follow-up

The study participation will be considered completed after the 90 day follow up visit has been completed. If for any reason the patient cannot visit the clinic/hospital for the follow up, the Investigator or research staff should ask permission from the patient and family if an in-person visit could take place at the current dwelling facility to assess patient's neurological condition. In the event that in-person assessment is not possible, research team-members should conduct a phone interview. In the event that the patient cannot be reached or is unable to answer assessment questions, their caregiver or family member can be questioned.

The patient's quality of life will be assessed using the EQ-5D provide a numerical measure of the patient's health utility. In the event the patient is unable to communicate or understand the questions, his/her next of kin (proxy) who knows the most about their current health state will be asked to fill out these questionnaires on behalf of the patient. Importantly, the proxy will be instructed to fill answer the quality of life questionnaires from the patient's perspective – knowing everything they know about the patient, how would they answer if they capable.

7.0 ANESTHESIA GUIDANCE

7.1 Sedation

Sedation will be provided under the supervision of an anesthesiologist using a combination of fentanyl, midazolam, dexmedetomidine infusion (with or without loading dose), remifentanil infusion, and/or low-dose propofol by intermittent bolus or infusion, with a target Richmond Agitation Sedation Scale (RASS) score of -1 to -3 (light to moderate sedation – responds to verbal stimulation; see Appendix II).

Sedation patients who do not tolerate sedation (e.g., patient agitation, airway difficulty, loss of consciousness, aspiration, cardiovascular instability) should be converted to Inhalational GA and the corresponding protocol followed.

7.2 General Anesthesia

Induction of anesthesia will be achieved with propofol and/or etomidate; muscle paralysis with succinylcholine or non-depolarizing paralytic (rocuronium or vecuronium); and adjuvant lidocaine and fentanyl as deemed appropriate by the anesthesiologist. Hyperventilation should be avoided during induction.

Intravenous: Maintenance of anesthesia will be achieved by propofol infusion at 50 to 150 mcg/kg/min with redosing of non-depolarizing paralytic and fentanyl (and/or remifentanil infusion) as needed.

Inhalational: Maintenance of anesthesia will be achieved with sevoflurane 1% to 2% or desflurane 3% to 6% end-tidal concentration with redosing of non-depolarizing paralytic and fentanyl (and/or remifentanil infusion) as needed.

7.3 Blood Pressure Management

Systolic blood pressure (SBP) should be maintained at 140 to 180 mmHg with pressors (e.g., phenylephrine, norepinephrine) or antihypertensives (e.g., nicardipine, labetalol) as needed. Diastolic blood pressure should be maintained <105 mmHg.

In patients who are reperfused after EVT (defined as achieving TICI 2b or TICI 3), SBP should be maintained at 140 mmHg in the first 24 hours to minimize the risk of reperfusion-related brain hemorrhage. Blood pressure of patients who fail to achieve recanalization will be left to the discretion of the individual stroke centers' usual care.

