3.4 Exploratory Analyses

- 1) Ordinal ITT and as-treated analysis of primary outcome comparing three groups (CS, GA IV, GA inhalational) adjusting for stratification variables.
- 2) Multivariable adjusted analysis (including stratification variables) for both primary (mRS 0-2) and ordinal analysis of 90-day mRS outcomes, to include (but not limited to) baseline variables known to be clinically associated with stroke outcomes:
 - a. Age
 - b. NIHSS
 - c. Time from stroke onset-to-EVT groin puncture
 - d. IV-tPA treatment before EVT
 - e. Atrial Fibrillation
- 3) Duration of time during EVT spent below a systolic blood pressure of 140mmHg.
- 4) Total ICU and ventilator days.
- 5) Subgroup analyses to test for heterogeneity in patient benefit and Provider Skill:
 - a. Proximal vs. Distal occlusion location (ICA+M1-MCA vs. others)
 - b. High-volume vs. low-volume centers
- 6) Costs from a health system perspective

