7.4 Anesthesia Monitoring

Invasive hemodynamic monitoring should be attempted prior to induction of GA to allow for tight hemodynamic control. To limit any delay in time to revascularization, attempts to establish peripheral invasive arterial access should be limited to 5 minutes; after that time, continuously-cycled non-invasive blood pressure measurements should be performed until invasive hemodynamic monitoring can be achieved through the femoral sheath. SBP should be maintained at 140 to 180 mmHg throughout with phenylephrine and/or norepinephrine as needed. Patients who are converted from sedation who already have invasive hemodynamic monitoring through the femoral sheath do not need additional arterial access.

End-tidal CO₂ concentration (PETCO₂) in patients receiving GA should be maintained at 35 to 40 mmHg (corresponding to a PaCO₂ ~40-45 mmHg).

All patients who are deemed medically appropriate for extubation should be awakened and extubation attempted at the conclusion of the procedure. Muscle paralysis should be reversed at the conclusion of the procedure using neostigmine or sugammadex; those patients with deep neuromuscular blockade that precludes reversal with neostigmine should be reversed with an adequate dose of sugammadex to avoid unnecessary prolonged intubation.

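### Sections 7.3 and 7.4 give different systolic pressure instructions for a reperfused patient still under anesthesia, and 7.3 does not say what kind of limit its 140 mmHg is

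*Combined protocol and SAP*

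**What the plan says.** Section 7.3 opens with a general rule that has no time window: "Systolic blood pressure (SBP) should be maintained at 140 to 180 mmHg with pressors" or antihypertensives. Its second paragraph turns to patients with TICI 2b or 3 and says "SBP should be maintained at 140 mmHg in the first 24 hours to minimize the risk of reperfusion-related brain hemorrhage". No inequality, range or tolerance is given, and no start for the 24 hours. For the remaining patients: "Blood pressure of patients who fail to achieve recanalization will be left to the discretion of the individual stroke centers' usual care".

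Section 7.4, on anesthesia monitoring, says "SBP should be maintained at 140 to 180 mmHg throughout with phenylephrine and/or norepinephrine as needed". It names pressors only and makes no exception once the vessel is open. The sentence comes after "Invasive hemodynamic monitoring should be attempted prior to induction of GA to allow for tight hemodynamic control" and before a sentence on patients converted from sedation. The section closes with the patient who "should be awakened and extubation attempted at the conclusion of the procedure".

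Section 3.4, item 3, lists an exploratory measure: "Duration of time during EVT spent below a systolic blood pressure of 140mmHg". Section 7.5 takes the pressures for it from the electronic anesthetic record. Section 6.2.1 records time to revascularization, from arterial puncture to TICI 2b or better, or to the end of the procedure.

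**The concern.** A patient can reach TICI 2b or 3 while still anesthetized. From that moment 7.3 gives one figure, 7.4 gives a range 40 mmHg wide, and neither section says which prevails. The 7.3 figure is also unclear by itself for the full 24 hours, because a bare value can be read as a ceiling, a floor or a center.

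The stated purpose of the 7.3 sentence is to limit hemorrhage. Symptomatic intracerebral hemorrhage is a safety endpoint in section 3.3. Intracerebral hemorrhage within 18-36 hours is, with death, an endpoint of the interim safety analyses in section 9.4, where a posterior probability of harm above 97.5% may lead the DSMB to consider termination. An instruction aimed at that outcome should have one meaning.

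There is a smaller effect on measurement. The exploratory measure uses the same 140 mmHg as its cut-off. If it includes time after reperfusion, its meaning there depends on how 7.3 is read.

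**Working it through.** The plan states no figure that depends on this point, so there is nothing to reproduce. The check is mainly a comparison of texts.

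**Periods covered.** Section 7.4 runs from before induction to extubation at the end of the procedure, so *throughout* most naturally means throughout the anesthetic. The second paragraph of 7.3 covers 24 hours in reperfused patients. The two periods are largely successive. If the 24 hours start at reperfusion, they overlap from TICI 2b/3 until anesthesia ends. Section 6.2.1 implies that such an interval can exist, since it treats reaching TICI 2b and the end of the procedure as separate time points. Its length is not given.

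**Compatibility within the overlap**, for each meaning that 140 mmHg in 7.3 could have:

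| 140 in 7.3 read as | Readings that meet both 7.3 and 7.4 | Where the sections diverge |
|---|---|---|
| Single target value | 140 only | Above 140 to 180: meets 7.4, not 7.3 |
| Upper limit | 140 only | Above 140 to 180: meets 7.4, not 7.3. Below 140: meets 7.3, not 7.4 |
| Lower limit | 140 to 180 | Nowhere in that range |

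Only the lower-limit reading removes the conflict. It is also the reading that fits the sentence least, because it calls for raising pressure in a reperfused patient below 140 as a way to limit hemorrhage.

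**Arms covered.** The first paragraph of 7.3 is general. The 7.4 sentence stands between one about induction of GA and one about conversion from sedation, so it could be read as applying to GA patients only or to everyone.

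**Patients under the 7.3 instruction.** Inputs: reperfusion of 89% (GA) and 81% (sedation) in the earlier single-center randomized trial (section 1.2), and 130 patients per arm (section 9.1).

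- GA: 0.89 × 130 = 115.7, about 116
- Sedation: 0.81 × 130 = 105.3, about 105
- Total: about 221 of 260, or 85%
- With either rate applied to all 260: 0.81 × 260 = 211 to 0.89 × 260 = 231

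This assumes that SEGA reperfuses at the earlier trial's rates.

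**Time below 140 mmHg.** The documents give no distribution of systolic pressure, so the following is illustrative. Assume normal readings with SD 10 to 15 mmHg. The share below 140 is Φ((140 − mean)/SD).

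- Mean 140: Φ(0) = 50%
- Mean 160 (middle of the range): Φ(−2.0) = 2% at SD 10; Φ(−1.33) = 9% at SD 15. Gap from 50%: 48 and 41 percentage points
- Mean 145: Φ(−0.5) = 31% at SD 10; Φ(−0.33) = 37% at SD 15. Gap: 19 and 13 points

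The gap runs from 13 to 48 points according to the assumed mean and SD. It concerns only the part of the procedure after reperfusion.

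**The case against.** The strongest reply is that the rules are sequential. Section 7.4 governs the anesthetic, and the second paragraph of 7.3 governs recovery in patients reperfused after EVT. For most of the 24 hours only 7.3 applies, and if its clock starts at the end of the procedure there is no overlap with 7.4. This stands as a limit on scope. It does not remove the problem, because the start of the 24 hours is not stated, 7.4 has no exception, and the bare value remains unclear after the procedure too.

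A reader might infer that the two sections can never be followed together. That goes too far: a reading of 140 satisfies both.

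A reader might also infer that sites would manage most patients differently. The documents do not support this. The 221 are patients expected to come under the instruction, and nothing shows how sites read it. Randomization is stratified by center (section 4.2) and center is a random effect in the models (section 9.2), so a site's own reading would tend to fall on both of its arms. The possible GA-only reading of 7.4 is an exception, but the documents do not show that any site takes it.

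Finally, a reader might take the larger gap in time below 140 mmHg as the effect on the trial. It depends on an assumed mean of 160, while 7.4 gives a range and directs nobody to its middle. Nor do sections 3.4 and 7.5 classify anyone as hypotensive; they record time below a value, for one exploratory item.

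**Conclusion.** The wording needs correction. Two defects stand on the text alone:

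- 7.3 and 7.4 diverge for a reperfused patient still under anesthesia, at readings above 140 up to 180 mmHg, unless 140 is read as a floor.
- The single value in 7.3 has no stated type of limit and no stated start for its 24 hours.

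About 221 of 260 patients (211 to 231) would come under the 7.3 instruction if reperfusion matches the earlier trial. The direct clash is confined to the interval between reperfusion and the end of anesthesia, whose length is unknown. Neither divergent practice nor an effect on hemorrhage can be quantified from the documents. The primary analysis and the sample size are unaffected. The case for acting is that the instruction bears on a safety and interim-monitoring endpoint and is cheap to clarify.

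**What to change.** The sponsor and its clinical leads should reconcile 7.3 and 7.4 and state:

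- which instruction applies from the moment TICI 2b or 3 is reached;
- when the 24 hours start;
- how far *throughout* in 7.4 reaches, and in which arms;
- whether the 7.3 figure is an upper limit, a lower limit, a range or a target.

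The values are theirs to choose; none is proposed here.

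For the measure in section 3.4, item 3, keep time with systolic pressure below 140 mmHg over the whole procedure, and also report it split before and after reperfusion. The revascularization time in section 6.2.1 and the anesthetic record in section 7.5 already supply what is needed. Ending the count at reperfusion is not advised: it would truncate the measure at a post-randomization event that may differ by arm. For the same reason the split should be treated as descriptive.

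Cost: a protocol wording change, a memo to sites and one extra descriptive table. No new data are needed.
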